2.7 Analysis of the primary variable

The primary objective is to demonstrate the antitumor activity of INC280, as measured by overall response rate (ORR) to INC280 by Blinded Independent Review Committee (BIRC) assessment, by cohort.

2.7.1 Variable

The primary variable used to evaluate the anti-tumor activity of INC280 is the overall response rate (ORR), defined as the proportion of patients with a best overall response (BOR) as complete response (CR) or partial response (PR), as assessed per RECIST 1.1 by BIRC.

Best overall response (BOR)

The BOR will be assessed based on reported lesion responses at different evaluation time points. Both CR and PR must be confirmed by repeat assessments performed not less than 4 weeks after the criteria for response are first met. The next scheduled assessment may be used for purposes of confirmation of response.

BOR for each patient is determined from the sequence of overall (lesion) responses according to the following rules:

- CR = at least two determinations of CR at least 4 weeks apart before progression
- PR = at least two determinations of PR or better at least 4 weeks apart before progression (and not qualifying for a CR)
- SD = at least one SD assessment (or better) > 6 weeks after start of study drug (and not qualifying for CR or PR).
- PD = progression ≤ 12 weeks after start of study drug (and not qualifying for CR, PR or SD).
- UNK = all other cases (i.e. not qualifying for confirmed CR or PR and without SD after more than 6 weeks or progression within the first 12 weeks)

Only tumor assessments performed before the start of any further anti-neoplastic therapies (i.e. any additional secondary anti-neoplastic therapy or anti-cancer surgery) and within 30 days after the last dose of study treatment will be considered in the assessment of BOR.

Local bone radiotherapy for analgesic purposes or for lytic lesions at risk of fracture are not considered secondary anti-neoplastic therapy. If a patient receives any further anti-neoplastic therapy while on study, any subsequent assessments will be excluded from the BOR determination. Further anti-neoplastic therapies will be identified via protocol deviations or from the data collected on 'Anti-neoplastic therapies since last date of study drug' as appropriate. Palliative radiotherapy in the bone is the only setting of radiotherapy allowed during the study. Therefore palliative radiotherapy in the bone will not be considered as an anti-neoplastic therapy for assessment of BOR.

Clinical deterioration will not be considered as documented disease progression.

Patients with BOR 'unknown' will be summarized by reason for having unknown status. The following reasons will be used:

- No valid post-baseline assessment
- All post-baseline assessments have overall response UNK
- New anti-neoplastic therapy started before first post-baseline assessment
- Stable disease (SD) too early (≤ 6 weeks after start date of study drug*)
- PD too late (> 12 weeks after start date of study drug*)

Special (and rare) cases where BOR is 'unknown' due to both early SD and late PD will be classified as 'SD too early'.

*Thresholds for SD too early and PD too late are defined as the protocol-specified time interval + protocol-allowed time windows (± 4 days) around the tumor assessments.

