### 6.4.1 Permitted concomitant therapy

Patients are permitted to use the following medications while taking INC280:

- Oral or topical antibiotics
- Medications to prevent or treat nausea, vomiting or diarrhea
- Growth factors (e.g. G-CSF, GM-CSF, erythropoietin, platelets growth factors, etc.) are allowed per the investigator's judgement and per local guidelines.
- Treatment with bisphosphonates for pre-existing bone metastases is permitted, if clinically indicated, and following existing local guidelines. Treatment with bisphosphonates should preferably begin before the study treatment is initiated, but can also be initiated during therapy only if absence of radiological bone disease progression is well documented (in this case, the reason for its use must be clearly documented; i.e. "pre-existing, non-progressing, bone metastases").
- Oxygen therapy and blood products or transfusions
- Nutritional support or appetite stimulants
- Pain medication
- Local bone radiotherapy for analgesic purposes or for lytic lesions at risk of fracture may be carried out if required. If palliative radiotherapy is initiated after start of study treatment, the reason for its use must be clearly documented and progression as per RECIST 1.1 must be ruled out. The study treatment must be interrupted on the days of radiotherapy and can be resumed the day after its completion.

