#### Imaging requirements at baseline

- Patients must have measurable disease as per RECIST 1.1 ([Appendix 1](#)). Measurable (“target”) lesions include lytic or mixed (lytic + blastic) bone lesions with an identifiable soft tissue component that meets the measurability criteria per RECIST 1.1 ([Appendix 1](#)).
- Patients with only non-measurable lesions are not eligible.

- If the measurable disease is restricted to a solitary lesion, its neoplastic nature should be confirmed by cytology/histology.
- Any potentially measurable lesion that has been previously treated with radiotherapy should be considered as a non-measurable (“non-target”) lesion. However, if a lesion previously treated with radiotherapy has clearly progressed since the radiotherapy, it can be considered as a measurable lesion.

All measurable lesions up to a maximum of 5 nodal and/or non-nodal lesions in total (and a maximum of 2 lesions per organ), representative of all involved organs, should be identified as target lesions and recorded and measured at baseline.

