#### **Measurable lesions (both nodal and non-nodal)**

- Measurable non-nodal - As a rule of thumb, the minimum size of a measurable non-nodal target lesion at baseline should be no less than double the slice thickness or 10mm whichever is greater - e.g. the minimum non-nodal lesion size for CT/MRI with 5mm cuts will be 10 mm, for 8 mm contiguous cuts the minimum size will be 16 mm.
- Lytic bone lesions or mixed lytic-blastic lesions with identifiable soft tissue components, that can be evaluated by CT/MRI, can be considered as measurable lesions, if the soft tissue component meets the definition of measurability.
- Measurable nodal lesions (i.e. lymph nodes) - Lymph nodes  $\geq 15$  mm in short axis can be considered for selection as target lesions. Lymph nodes measuring  $\geq 10$  mm and  $< 15$  mm are considered non-measurable. Lymph nodes smaller than 10 mm in short axis at baseline, regardless of the slice thickness, are normal and not considered indicative of disease.

- **Cystic lesions:**

- Lesions that meet the criteria for radiographically defined simple cysts (i.e., spherical structure with a thin, non-irregular, non-nodular and non-enhancing wall, no septations, and low CT density [water-like] content) should not be considered as malignant lesions (neither measurable nor non-measurable) since they are, by definition, simple cysts.
- ‘Cystic lesions’ thought to represent cystic metastases can be considered as measurable lesions, if they meet the definition of measurability described above. However, if noncystic lesions are present in the same patient, these are preferred for selection as target lesions.

**Non-measurable lesions** - all other lesions are considered non-measurable, including small lesions (e.g. longest diameter <10 mm with CT/MRI or pathological lymph nodes with  $\geq 10$  to < 15 mm short axis), as well as truly non-measurable lesions e.g., blastic bone lesions, leptomeningeal disease, ascites, pleural/pericardial effusion, inflammatory breast disease, lymphangitis cutis/pulmonis, abdominal masses/abdominal organomegaly identified by physical exam that is not measurable by reproducible imaging techniques.

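### SAP 2.7.1 ignores palliative bone radiotherapy for best overall response even when the irradiated lesion is a RECIST target, so radiation shrinkage may count toward the primary ORR

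*SAP*

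**What the plan says.** SAP 2.7.1 removes from BOR any scan taken after a new cancer treatment: "If a patient receives any further anti-neoplastic therapy while on study, any subsequent assessments will be excluded from the BOR determination". Bone radiotherapy is exempted: "Local bone radiotherapy for analgesic purposes or for lytic lesions at risk of fracture are not considered secondary anti-neoplastic therapy". The SAP reasons that palliative bone radiotherapy is the only kind allowed on study, and concludes: "Therefore palliative radiotherapy in the bone will not be considered as an anti-neoplastic therapy for assessment of BOR".

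Protocol 6.4.1 permits the treatment: "Local bone radiotherapy for analgesic purposes or for lytic lesions at risk of fracture may be carried out if required". If it starts after study treatment has begun, the reason must be documented and "progression as per RECIST 1.1 must be ruled out". Nothing requires the irradiated lesion to be a non-target lesion.

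Protocol 7.2.1.1 accepts as targets lytic or mixed "bone lesions with an identifiable soft tissue component that meets the measurability criteria per RECIST 1.1". Appendix 14.1.4 agrees: "Lytic bone lesions or mixed lytic-blastic lesions with identifiable soft tissue components, that can be evaluated by CT/MRI, can be considered as measurable lesions", provided the soft-tissue part is measurable.

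For radiotherapy before study entry, protocol 7.2.1.1 says: "Any potentially measurable lesion that has been previously treated with radiotherapy should be considered as a non-measurable" lesion, unless it has clearly progressed since. Inclusion criterion 5 says the same in substance.

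**The concern.** The protocol recognises at baseline that an irradiated lesion is a poor measure of drug effect. That protection stops at the first dose. From then on a bone target can be irradiated, its later measurements remain usable, and the SAP keeps the scans in BOR. That the treatment is permitted does not mean it leaves a measured lesion unaffected.

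ORR by BIRC is the primary endpoint and there is no control arm, so a response produced by a local co-intervention enters the numerator directly. Appendix 14.1.17 would ordinarily drop assessments made after alternative cancer therapy and asks for a justification in the protocol if they are kept.

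**Working it through.** **Does any written rule catch the case?**
- Table 14-1 defines PR as a fall of at least 30% in the sum of target diameters, whatever the cause.
- The target category UNK in Table 14-1 covers lesions not assessed or assessed by a different method. Irradiation is not named.
- The notes in Appendix 14.1.12 cover reappearance, missing measurements, nodes, splitting and merging, but not irradiation.
- The waterfall rules in SAP 4.6.1 do not mention it either.

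So neither document has a lesion-level rule for a target irradiated after the first dose.

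**How much shrinkage is needed?** If all other targets are unchanged and the irradiated lesion makes up a share f of the baseline sum, a PR needs that lesion to shrink by 0.30/f.
- f = 1/2: 60%. Illustration: lung 40 mm plus rib mass 40 mm = 80 mm. The rib mass falls to 16 mm, the sum is 56 mm, and 56/80 − 1 = −30%.
- f = 3/4: 40%.
- f = 1 (sole target): 30%.
- f below 0.30: 0.30/f exceeds 1, so radiation alone cannot give a PR.

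The response must also be confirmed at least 4 weeks later, with no new lesion and no non-target progression.

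**The plan's own figures, reproduced.** Exact (Clopper-Pearson) lower limits: 15/27 gives 35.3% (Table 10-6: 35.3) and 25/69 gives 24.995% (Table 10-5: 25.0). Table 10-9 at true ORR 55%, P(X ≥ 15 of 27): 55.62% (stated 55.6). Table 10-7 (stop at 7 or fewer of 28, succeed at 25 or more of 69): 2.34% at true ORR 25% and 44.00% at 35%, both as stated.

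**Value of one response**
- 1/27 = 3.7 points; 1/69 = 1.4 points.
- 27 patients, bound 35%: 15/27 has lower limit 35.3% and passes; 14/27 has 32.0% and fails.
- 69 patients, bound 25%: 26/69 has 26.3% and passes; 25/69 has 24.995% and strictly fails.

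**Sensitivity (m is assumed; the documents give no frequency).** If each true non-responder has probability m of a false response by this route, the observed ORR is p0 + (1 − p0)m. At m = 2% this is 0.25 + 0.75 × 0.02 = 0.265, or 0.35 + 0.65 × 0.02 = 0.363. The chance of a positive result when the true ORR equals the null value is then:

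| m | 69 patients, null 25% (Table 10-7 rule) | 27 patients, null 35% |
|---|---|---|
| 0% | 2.34% | 2.29% |
| 1% | 3.29% | 2.72% |
| 2% | 4.52% | 3.21% |
| 3% | 6.06% | 3.77% |
| 5% | 10.26% | 5.10% |

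**Direction for progression.** PD is judged from the smallest sum. In the illustration, without radiotherapy the lung lesion must grow 0.20 × 80 = 16 mm for PD. After radiotherapy lowers the sum to 56 mm, 0.20 × 56 = 11.2 mm is enough. A lower nadir can therefore bring PD forward, while local control of the bone lesion can delay it.

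**The case against.** The strongest reply is that the primary ORR is not computed from diameters under SAP rules. SAP 4.6.2 takes the overall lesion response reported by BIRC, and Appendix 14.1.32 says the central reader's assessment is never overruled. The reading rules are in a charter outside these documents. Appendix 14.1.10 also lets a reader leave a lesion unmeasured when it cannot be measured reliably for reasons other than size, which makes the overall response unknown unless there is PD. This stands as a limit: the charter may close the gap. Neither document says that it does, or that radiotherapy dates and sites are sent to BIRC.

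Second, the illustration sits exactly on the threshold, and no document gives the frequency of such irradiation or the shrinkage it produces. This also stands. Nor should a reader infer that results already reported depend on radiation. The preliminary figures in protocol 1.2.1.2.2 are 39.1% of 69 (27 responders) and 72.0% of 25 (18 responders). Removing one leaves lower limits of 26.3% (26/69) and 46.5% (17/25), both above their bounds. Reversal would take two responses in Cohort 4 (25/69, 24.995%) and four in Sub-cohort 5b (14/25, 34.9%).

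Third, a reader might infer that the bias always favours INC280 and also lengthens DOR and PFS. The documents do not support this. The lowered nadir works the other way, and the SAP 2.7.1 sentence governs BOR only. For DOR and PFS, SAP Table 2-1 situation F ignores all new anticancer therapy by separate design.

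**Conclusion.** The gap is real but narrow. A stated SAP rule keeps scans taken after bone radiotherapy in BOR, bone lesions can be targets, and neither document has an exception for an irradiated target. Unless the BIRC charter has one, radiation shrinkage can count toward a confirmed PR or CR in the primary ORR. For ORR, a false response of this kind can only add to the numerator.

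The size cannot be fixed from the documents. It matters mainly where bone is a large part of the target disease, and the frequency is probably low; the values of m above are assumptions. What is certain is the value of one response, and that a single one can decide a cohort at the boundary. The point does not challenge the stated power or sample size, does not show that any reported response was caused by radiation, and makes no claim about the net effect on DOR or PFS. It is worth correcting because the correction is cheap and concerns the primary endpoint.

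**What to change.** Change the analysis only; when radiotherapy may be given is not at issue.

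- In SAP 2.7.1, keep ignoring bone radiotherapy when no target lesion is in the field.
- When a target lesion is irradiated on study, assessments after that date may not first establish CR or PR. They may still show PD or confirm a response first met before radiotherapy.
- Report the number of patients with an irradiated target. If it is zero, one sentence closes the question.
- Add a sensitivity ORR that counts responses first met or confirmed after target irradiation as non-responses.
- Flag these patients in the waterfall plot.
- Leave the DOR and PFS censoring rules unchanged.

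Scoring every later scan as UNK would be simpler but harmful. SAP 4.6.1 treats UNK as a missing assessment, so a later progression more than 14 weeks after the last adequate scan would be censored under Table 2-1 situation C2. A PR first met before radiotherapy could also go unconfirmed and become a non-response.

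Primary analyses have been run, but SAP 2.1 plans updated efficacy for Cohorts 4, 5b, 6 and 7, where the change can still be made. The cost is SAP wording, a programming flag linking radiotherapy site and date to the target lesions, and one extra table. The downside is that a few genuine responders may be lost, so ORR may be slightly lower.

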2.7.2 Statistical hypothesis, model, and method of analysis

The primary analysis will be performed on the FAS. The primary efficacy endpoint ORR will be estimated and the exact 95% confidence interval (CI) ([Clopper and Pearson 1934](#)) provided by cohort.

Treatment with INC280 will be considered to have clinically relevant efficacy in cohort (1-4) if an ORR of $\sim 35\%$ is observed in that cohort with lower bound of exact 95% CI greater than 25%. Whereas, in cohorts (5a and 5b and 7), treatment with INC280 will be considered to have clinically relevant efficacy if an ORR of $\sim 55\%$ is observed in that cohort with lower bound of exact 95% CI greater than 35%.

No hypothesis testing is planned for cohort 6.

2.7.3 Handling of missing values/censoring/discontinuations

Confirmed PR or CR reported prior to any additional anticancer therapy will be considered as responses in the calculation of the ORR irrespective of the number of missed assessments before response.

Patients with a BOR of 'Unknown' per RECIST 1.1 will be considered as non-responders when estimating ORR.

Patients with no BIRC data will be considered as non-responders when estimating ORR.

Patients who have disease progression and continue to receive study drug after progression will qualify for PD at the time of progression and will be counted as PD in the derivation of ORR and any other efficacy endpoints.

2.7.4 Supportive analyses

ORR by BIRC will be presented combining the MET mutant cohorts per line of treatment as defined in [Section 2.2](#).

ORR by BIRC will be summarized by subgroup (as defined in [Section 2.2](#)). Forest plot (including sample size/number of responders and ORR with 95% CI) will be produced to graphically depict the treatment effect estimates in different subgroups.

In addition, the primary analysis will be repeated on the PPS.

Waterfall plots representing the best percentage change from baseline in the sum of the tumor measured diameters for target lesions will be produced by cohort.

ORR by BIRC according to the accepted radiologist who was chosen at the time of the submission will be produced as per FDA request (Previous Radiologist Accepted flag: PRARDF): radiologist chosen at the data cut-off 15-Apr-2019 for NDA submission in Cohorts 4 and 5b and at the data cut-off 30-Aug-2021 for Post-Marketing Requirements (PMR) in Cohorts 6 and 7.

2.8 Analysis of secondary variables

2.8.1 Efficacy

All secondary endpoint analyses will be performed based on the FAS, unless otherwise specified. Efficacy will also be presented combining the MET mutant cohorts per line of treatment as defined in [Section 2.2](#).

No adjustment for multiple testing will be made.

Key secondary efficacy endpoints

The key secondary objective is to evaluate duration of response (DOR) as assessed by BIRC, by cohort.

Among patients with a confirmed response (PR or CR), DOR is defined as the time from first documented response (PR or CR) to the date of first documented PD or death due to any cause. If a patient has not had an event, DOR is censored at the date of last adequate tumor assessment.

The censoring and event date options to be considered for the main analysis are presented in [Table 2-1](#).

Table 2-1 Outcome and event dates for DOR and PFS analyses

Situation	Date	Outcome
A No baseline assessment	Date of first dose of study drug ^a	Censored
B Progression at or before next scheduled Assessment	Date of progression	Progressed
C1 Progression or death after exactly one missing assessment	Date of progression (or death)	Progressed
C2 Progression or death after two or more missing assessments	Date of last adequate assessment	Censored
D No progression	Date of last adequate assessment	Censored
E Treatment discontinuation due to 'Disease progression' without documented progression, i.e. clinical progression based on investigator claim	N/A	Information ignored. Outcome derived based on radiology data only.
F New anticancer therapy given	Ignore the new anticancer therapy and follow situations above	As per above situations
G Deaths due to reason other than deterioration of 'Study indication'	Date of death	Progressed

^a The rare exception to this is if the patient dies no later than the time of the second scheduled assessment as defined in the protocol in which case this is a PFS event at the date of death

DOR will be described in tabular and graphical format using Kaplan-Meier methods. The Kaplan-Meier estimate of the distribution function will be constructed. Kaplan-Meier curves

will be constructed. The number of patients at risk at certain time points will be shown on the plot. The estimated median (in months) along with 95% CIs, as well as 25th and 75th percentiles will be reported ([Brookmeyer and Crowley 1982](#)). In addition, Kaplan-Meier estimated probabilities with corresponding 95% CIs at several time points (including at least 3, 6, 12, and 18 months) will be summarized. Refer to [Section 4.6.3](#) for further details regarding derivation of Kaplan-Meier estimates.

Supportive analysis

DOOR by BIRC will also be presented combining the MET mutant cohorts per line of treatment as defined in [Section 2.2](#).

DOOR by BIRC assessment will be summarized by subgroup (as described in [Section 2.2](#)).

Supportive analysis of DOOR table by BIRC assessment based on the PPS will also be presented.

DOOR by BIRC according to the accepted radiologist who was chosen at the time of the submission will be produced as per FDA request (Previous Radiologist Accepted flag: PRARDF): radiologist chosen at the data cut-off 15-Apr-2019 for NDA submission in Cohorts 4 and 5b and at the data cut-off 30-Aug-2021 for Post-Marketing Requirements (PMR) in Cohorts 6 and 7.

ORR by investigator assessment

The evaluation of ORR will be also conducted based on investigator assessment. ORR will be estimated and the exact binomial 95% CI will be provided by cohort.

ORR by investigator will be summarized by subgroup (as defined in [Section 2.2](#)) and forest plot will be produced.

A summary table will also be produced for BOR based on investigator assessment versus BIRC assessment. An assessment of the concordance between BIRC assessment and local assessment of the Best Overall Response for each patient will be provided by cohort. Overall concordance rate in each cohort is calculated as (number of patients with same BORs per investigator and per BIRC)/(total number of patients in that cohort).

DOR by investigator assessment

Among patients with a confirmed response (PR or CR), DOR is defined as the time from first documented response (PR or CR) to the date of first documented PD or death due to any cause. If a patient has not had an event, DOR is censored at the date of last adequate tumor assessment.

The censoring and event date options to be considered for the main analysis are presented in [Table 2-1](#).

DOR will be described in tabular and graphical format using Kaplan-Meier methods by cohort. The Kaplan-Meier estimate of the distribution function will be constructed. Kaplan-Meier curves will be constructed. The number of patients at risk at certain time points will be shown on the plot. The estimated median (in months) along with 95% CIs, as well as 25th and 75th percentiles will be reported ([Brookmeyer and Crowley 1982](#)). In addition, Kaplan-Meier estimated probabilities with corresponding 95% CIs at several time points (including at least 3, 6, 9, 12 and 18 months) will be summarized by cohort. These analyses will be performed

separately based on BIRC assessment and based on investigator assessment. Refer to [Section 4.6.3](#) for further details regarding derivation of Kaplan-Meier estimates.

Disease control rate (DCR)

DCR is defined as the proportion of patients with best overall response of CR, PR, or SD per RECIST 1.1. DCR will be estimated and the binomial exact 95% CI will be provided by cohort. These analyses will be performed separately based on BIRC assessment and based on investigator assessment.

Time to response (TTR)

TTR is defined as the time from start of study drug to first documented response (CR or PR, which must be confirmed subsequently) for patients who achieved a confirmed PR or CR. All patients in the FAS will be included in time to response calculations. Patients who did not achieve a confirmed PR or CR, will be censored at:

- the maximum follow-up time (i.e. first patient first treatment to last patient last treatment by cohort used for the analysis) for patients who had a PFS event (i.e. either progressed or died due to any cause), or at the date of last adequate tumor assessment date otherwise.

TTR will be summarized in 6-weeks intervals using descriptive statistics. The distribution of time to response will be estimated using the Kaplan-Meier method and the median time to response will be presented along with 95% confidence interval only if a sufficient number of responses is observed. Failure curves (ascending Kaplan-Meier curves) will be constructed. These analyses will be performed separately based on BIRC assessment and based on investigator assessment.

Progression-free survival (PFS)

PFS is defined as the time from the start date of study drug to the date of the first radiologically documented PD or death due to any cause.

If a patient has not progressed or is not known to have died at the date of analysis cut-off, PFS will be censored at the date of the last adequate tumor evaluation before the cut-off date. PFS events documented after the initiation of new anti-neoplastic therapy (i.e. RECIST 1.1 documented disease progression or death) will be considered for the primary analysis provided tumor assessments continue after initiation of the new cancer therapy. Clinical deterioration will not be considered as a qualifying event for progression. Refer to [Table 2-1](#) for censoring and event date options and outcomes for PFS.

In particular, PFS will be censored at the last adequate tumor assessment if one of the following occurs: absence of event; the event occurred after two or more missing tumor assessments (see [Section 4.6.1](#)). See also [Section 4.6.1](#) describing the special case of a missing baseline tumor assessment.

Patients with no BIRC data will be considered censored at the start date of study drug.

PFS will be described in tabular and graphical format using Kaplan-Meier methods as described for DOR by cohort, including estimated median (in months) with 95% CI, 25th and 75th percentiles and Kaplan-Meier estimated probabilities with corresponding 95% CIs at several

time points. Censoring reasons will also be summarized by cohort. These analyses will be performed separately based on BIRC assessment and based on investigator assessment.

In addition, PFS table will be repeated on the PPS.

Overall survival (OS)

OS is defined as the time from the start date of study drug to the date of death due to any cause. If the patient is alive at the date of the analysis cut-off or lost to follow-up, then OS will be censored at the last contact date prior to data cutoff date (see [Section 4.3](#) for further details on derivation of last contact date).

OS will be described in tabular and graphical format using Kaplan-Meier methods as described for DOR by cohort, including estimated median (in months) with 95% CI, 25th and 75th percentiles and Kaplan-Meier estimated probabilities with corresponding 95% CIs at several time points. Censoring reasons will also be summarized by cohort.

OS from initial diagnosis to the date of death due to any cause will also be analyzed. Date of censoring is the same as defined for OS analysis.

Duration of Follow-up

Follow-up in the study will be summarized using the following methods to provide a comprehensive assessment of follow-up for all patients by cohort.

Summary of duration between start date of study drug and cut-off date, and follow-up times for PFS/OS/DOR, are defined as follows:

- Duration between start date of study drug and data cut-off date = (Cut-off date – Start date of study drug + 1) / 30.4375 (months).
- Follow-up time for PFS/OS = (Date of event or censoring – Start date of study drug + 1) / 30.4375 (months) regardless of censoring. Date of censoring is defined as the last adequate tumor assessment date for PFS or last contact date (when the patient is known as alive) for OS.
- Follow-up time for DOR = (Date of event or censoring – Start date of response + 1) / 30.4375 (months) regardless of censoring

Quartiles, minimum and maximum as well as the frequency count and percentage of patients in each of <1.5, 1.5-<3, 3-<6, 6-<9, 9-<12, ≥12 months will be reported for PFS, OS and DOR.

All summaries will be reported in months (see [Section 4.4](#)). The calculations for DOR and PFS will be based on BIRC assessment. Date of censoring is the same as defined for the DOR, PFS and OS analysis.

